Appendix 5. Consent and Assent forms	65

Summary

This document describes the protocol for evaluating an intervention to support adolescent girls from marginalised communities in northern Karnataka State, South India to complete secondary school, thereby reducing their vulnerability to HIV infection from early marriage and entry into sex work at young ages.

Overall purpose of the study

The purpose of this study is to evaluate the effectiveness of a multi-part intervention designed to influence adolescent girls (aged around 12-13) from Scheduled Castes and Scheduled Tribes in Northern Karnataka State, India, as well as their families, their schools and the communities in which they live. The intervention aims to improve multi-modal outcomes for these girls, especially the age at which they are married and the age at which they become active in sex work. While there are many pathways that the intervention aims to utilise to achieve these outcomes, the primary pathway is to keep girls in school.

Goal and objectives

The overall goals of the trial: to estimate the effect of a complex structural and behaviour change intervention on the percentage of adolescent girls who enter formal secondary education and the percentage of adolescent girls who complete standard 10. The effect will be estimated by randomizing village communities to either an intervention or a control arm and will use two cohort surveys of adolescent girls to measure the primary outcomes.

Study location

The trial will take place in Bijapur and Bagalkot districts in Northern Karnataka, India.

Study population

The main study population are SC/ST girls who have completed 7th standard, and will be approximately 13 years of age. Girls will be followed-up until they are approximately 16 years of age. Data will also be collected from the girls' parents and schools.

Study design

The study will use a cluster randomized trial design to estimate the effect of the intervention on the proportion of girls married before age 15, as well as other co-primary outcomes. The study will use a cohort of SC/ST girls as the primary data source for estimating effects, with a single endline follow up. Alongside the primary analysis, there will be extensive secondary analyses utilizing data collected in surveys of families and teachers, as well as qualitative data from a variety of stakeholders including boys in the community.

Existing literature on school drop outs and its consequences

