2. Assess the impact of the intervention on age at marriage, age at sexual debut and age of entry into sex work among adolescent SC/ST girls in schools and communities that have access to the intervention.
3. Explore how the intervention has affected the school and the communities' response to premature high school drop-out by SC/ST girls.
4. Investigate the processes and causal pathways through which positive changes occur in the following areas: support and value for education; self-esteem and confidence among adolescent girls; self-perceived safety and social status among adolescent girls and in their social networks; and culturally prescribed social expectations and gender norms.

Study components

This is a rigorous evaluation study that will be implemented by the Karnataka Health Promotion Trust (KHPT), based in Bangalore, Karnataka, in collaboration with the Social and Mathematical Epidemiology Group, London School of Hygiene and Tropical Medicine (LSHTM), and the Centre for

¹⁷ Standards 8, 9, 10.

Global Public Health, University of Manitoba, Canada. The project uses a cluster randomized, controlled trial (RCT) design, and has three main components:

1. A quantitative assessment involving two sequential cohort studies, one initiated in year 1 and another initiated in year 2, of a sample of SC/ST girls and their families at baseline and following the intervention.
2. A qualitative assessment documenting the process of implementation and change using qualitative methods with:
 - a. SC/ST girls
 - b. Families
 - c. Teachers
 - d. Community leaders
 - e. Policy makers
3. A robust monitoring system to monitor the intervention activities at school and community level.

Outcomes

Adolescent girls

This is a complex intervention which aims to act upon many modalities to affect change for SC/ST girls. For that reason we will be collecting a number of outcomes, many of which will be used to understand the effects observed in the primary and the secondary outcomes.

There are four **co-primary outcomes** on which the trial is sized:

1. Proportion of those enumerated in 7th standard (the study cohorts) who ENTER into grade 8th
2. Proportion of those in the study cohorts who complete 10th standard
3. Proportion of girls in the study cohorts who are married at end line.
4. Proportion of girls in the study cohorts who experienced first sexual intercourse at end line

The **secondary outcomes**:

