The study will employ a cluster randomized design. A cluster randomized design was chosen because the intervention is at a cluster level, i.e. many components of the intervention will not be delivered to specific individuals but to the schools and the communities where the individuals study and reside.

Site selection and cluster definition

The village is the unit of randomization. The village was chosen as the unit of randomization instead of the school so as to minimize the contamination between schools in the same village. In addition, some aspects of the intervention will act at the community level. In this setting, villages are sufficiently isolated so as to minimize contamination between villages.

Sampling of the adolescent girls

The project indicators for the SC/ST adolescent girls listed will be measured through two sequential cohort studies. Each SC/ST girl in the intervention and control clusters were profiled, This involved administering a brief questionnaire by trained outreach staff to the family of every listed SC/ST girl in

the study villages (control and intervention arms) to ascertain the girl's age, religion, family background and if they completed 7th standard. This information was used to help validate the denominator (ascertained through earlier mapping exercises) and to provide accurate data on the number of SC/ST girls attending and completing 7th standard school (the register lists provided by schools on SC/ST girls enrolled is frequently inflated). Girls will be invited to join the study at the end of 7th standard in year 1 (cohort 1) and year 2 (cohort 2), and each girl will be followed up until the start of year 4. By this point, most or all of the girls in both cohorts will have reached 15 years of age. By having two cohorts we can increase the available sample size and allow for the possibility that some of the intervention components will be more effective as they become established.

Sampling

Bijapur and Bagalkot district were pre-selected based on the high proportion of SC/ST girls in these districts, the programme rollout possibilities, existing infrastructure and rapport with the communities in these districts.

Enumeration of high schools

A high school enumeration was carried out by the existing project staff in these two districts. A standard format was developed to collect the information from these high schools with the following objectives;

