SC/ST girls will be enumerated and included in the cohort. We will conduct a complete-capture enumeration of all SC/ST girls in all trial sites, therefore, all SC/ST girls will be approached for inclusion in the trial.

Families

All families of SC/ST girls will be included in the cohort.

Sample size

The sample size calculations are based on the four co-primary outcomes:

1. Percentage of those enumerated in 7th standard (the study cohorts) who ENTER into grade 8th
2. Percentage of those in the study cohorts who complete 10th standard
3. Proportion of girls in the study cohorts who are married at end line.
4. Proportion of girls in the study cohorts who experienced first sexual intercourse at end line

The sample size calculations are based on the parameters shown in the table below. The baseline numbers are found in the KSS Karnataka report for 2010-2011, a rural assessment by KHPT in 2013, the district level household surveys (DLHS) from 2007-2008, and the Integrated Biological and behavioral Assessment (IBBA) conducted by KHPT from 2006-2011. Broadly speaking, the expected effect sizes are guided by the aim of the intervention to bring the outcomes among SC/ST girls in-line with all girls. Therefore, we have used the prevalence of the outcomes in these surveys to estimate plausible effect sizes.

Parameter	Notes
Harmonic mean cluster size	This is based on an enumeration carried out in the 225 high schools located in 121 villages by KHPT. Approximately 15 SC/ST girls are available at each school
Refusal/loss to follow-up	Refusal and loss to follow-up are expected to be low, approximately 5-10% (14 girls per cluster is used in the calculation, multiplied by 2 to account for the two cohorts)
Between cluster variation (k)	The between cluster variation in the outcomes is not known. Therefore, we have reported sample sizes for a range of values.
Control arm proportions	

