1-type I	Power	Control p	Cluster Size	% reduction	Intervention p	K	# clusters per arm
0.95	0.80	17%	28	30%	11.9%	0.15	30.4
						0.20	32.7
						0.25	35.6
						0.15	24.9
						0.20	26.7
						0.25	29.1
		33%		11.4%	0.15	40.0	
					0.20	42.3	
					0.25	45.2	
					0.15	32.7	
					0.20	34.5	
					0.25	36.9	
9%	5.9%	35%	28	35%	5.9%	0.15	41.7
						0.20	43.3

¹⁹ Hayes RJ and Bennett S, Simple sample size calculation for cluster-randomized trials, International Journal of Epidemiology, 1999; 28, 319-326

			45.4
		0.25	
			31.3
40%	5.4%	0.15	
			32.4
		0.20	
			33.9
		0.25	

Retention in school

We have reported a range of Risk Ratio minimum detectable effect sizes of RR=0.75-0.70. The lower effect size than for outcome 1 reflects the perception that this will be harder to influence with the intervention as the barriers to staying in school increase over time.

The *Sarva Shiksha Abhiyan Karnataka Analytical report 2010-11* (Education in Karnataka 2010-11) shows a higher dropout rate of SC/ST girls (22.5%) in transition from standard 8 to standard 10 compared to all girls (16.5%) in the state: this transition is an important stage in ensuring retention until the end of standard 10 and is how the 'retention' outcome will be actualized. The minimum detectable effect sizes of RR=0.75-0.70 are assumed on the basis that the intervention aims to bring retention of SC/ST girls in line with with the state average among all girls. The ratio between SC/ST girls and all girls of the dropout rates during transition from standard 8 to standard 10 is 0.73. This ratio is used as a indicator for the plausible effect of the intervention on retention to standard 10.

1-type I	Power	Control p	Cluster Size	% reduction	Intervention p	K	# clusters per arm			
0.95	0.80	40%	28	20%	32.0%	0.15	28.3			
						0.20	33.9			
						0.25	41.2			
		23%		30.8%	0.15	21.3				
					0.20	25.5				
					0.25	30.8				
		0.95		0.80	30%	28	20%	24.0%	0.15	38.8
									0.20	44.4
									0.25	51.7
23%	23.1%		0.15		29.1					
			0.20		33.3					
			0.25		38.6					
0.95	0.80		20%		28		23%	15.4%	0.15	44.8
									0.20	48.9
									0.25	54.2
		25%	15.0%	0.15		37.7				
				0.20		41.1				
				0.25		45.5				

Proportion married before age 15

The intervention will target marriage directly through school and home based interventions. Therefore, we aim to decrease the proportion married before 15 by 25-30%, corresponding to risk ratios of RR=0.75-0.70.

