Marriage	Current marital status, if married: (a) age at marriage (b) whether cohabiting with the husband, (c) if cohabiting, age at cohabitation
Sexual debut	Whether ever had sex, if yes, age at first sex
Entry into sex work	Whether ever received money in direct exchange for sex; if yes, age at first commercial sex
Entry into secondary school	School enrolment status
Continuation in secondary school	School attendance status, and school enrolment into 9 th and 10 standards
Quality education	Whether passed the previous standard
Medium-term outcomes	
Accessibility and expanded opportunities to enter and continue formal secondary education and job market	Respondents' perception of the availability and accessibility of secondary school education (cost, infrastructure, transport, distance, school environment, attitudes of teachers/schools) Respondents' perceptions of opportunities to secondary education (parents' support, support from the community/peers, livelihood and economic opportunities/job market after secondary education)
Sense of agency	Self esteem, self confidence, self-perceived safety and social status and increased social network
Short-term outcomes	
Aware of and access government schemes and subsidies	Whether aware of each of the existing government schemes/subsidies to encourage education; whether currently availing them, reasons for not availing the services
Attendance in tutorial classes	Whether aware of the mentoring and tutorials at school, and whether currently availing these services, reasons for not availing the services
Participation in group sessions of life skill education	Whether aware of group sessions conducted, whether they attended sessions and completed sessions

Participation in career counseling to enhance options after school completion	Whether aware of the career counselling, livelihood and life skill training at school, and whether currently availing these services, reasons for not availing the services
---	---

Table 5: Indicator domains and sub-domains that will be measured in the families of SC/ST adolescent girls at baseline and follow-up survey rounds in control and intervention villages, using a structured behavioural questionnaire.

Major domains	Minor domains

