During the start-up period, the baseline data collection instruments and protocols will be developed and finalized, and the data collection teams will be recruited and trained. The following three months will be devoted to baseline data collection. The last 9 months of the project will be devoted to end line data collection (three months), analyses and reporting (six months), and dissemination of the findings to the local communities, to Indian policymakers, and to the international community. Interim analyses will be conducted on a semi-annual basis, and a final report submitted upon completion of the project.

The diagram below shows when key study activities will take place (greyed boxes).

Year		2013		2014				2015				2016				2017				2018	
Quarter		3	4	1	2	3	4	1	2	3	4	1	2	3	4	1	2	3	4	1	2
Quantitative Studies																					
Cohort-1: Intervention & Control site																					
1	Girls																				
2	Family members of girls																				
Cohort-2: Intervention & Control site																					
1	Girls																				
2	Family members of girls																				
3	Principals, teachers and SDMC members																				
Qualitative Studies																					
1	Case studies (1st cohorts of girls from intervention and control, 2 nd and 3 rd cohort drop-outs from intervention)																				
2	IDI with girls, families, teachers, boys (intervention)																				
3	IDI- Champions																				
4	IDI- Policymakers																				
Intervention in intervention clusters																					

Ethical issues

Interviews will be conducted in private settings in a sensitive and non-judgmental manner. Since some of the participants will be minors, we will seek both written informed consent from the girl's parent or legal guardian (if she is unmarried) and informed assent of the girls. We will seek independent informed consent from girls who are married and living with their husband.

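### Co-primary outcome 3 is worded as current marital status, so an ended marriage reads as not married; this conflicts with the before-age-15 definition used for sizing, and neither outcome 3 nor 4 sets aside events before the intervention

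*Protocol*

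**What the plan says.** **Outcome wording.** The Outcomes section, repeated under Sample size, gives co-primary outcome 3 as "Proportion of girls in the study cohorts who are married at end line" and outcome 4 as "Proportion of girls in the study cohorts who experienced first sexual intercourse at end line". Both are taken over all girls in the study cohorts.

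**Data items.** The marriage row of Table 4 reads "Current marital status, if married: (a) age at marriage (b) whether cohabiting with the husband". The sexual debut row asks whether the girl has ever had sex and, if so, her age at first sex.

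**A second definition.** The Study design paragraph of the Summary says the trial will "estimate the effect of the intervention on the proportion of girls married before age 15, as well as other co-primary outcomes". The sizing subsection is headed "Proportion married before age 15", and outcome 4 is sized as intercourse before age 15.

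**Who enters.** Under Sampling frame, "therefore, all SC/ST girls will be approached for inclusion in the trial". On timing, "Girls will be invited to join the study at the end of 7th standard in year 1", with a second cohort a year later. The Summary puts girls at about 13 years at entry and about 16 at the end of follow-up. No section excludes a girl who is already married or sexually active. Ethical issues foresees married participants: "We will seek independent informed consent from girls who are married and living with their husband".

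**The concern.** The second study question concerns age at marriage and age at sexual debut. Two features of the wording fit it poorly.

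- **Reversal (outcome 3 only).** Current status can revert. An early marriage that ended in widowhood, separation or desertion would be scored as a success, and her age at marriage might not be recorded.
- **Events before the intervention (outcomes 3 and 4).** A girl with the event at entry is an event at end line whatever the intervention does. She moves the risk ratio towards 1 and uses up power.

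The two definitions of outcome 3 also count different girls. A marriage at 15 or 16 counts at end line but not before age 15. A marriage at 14 that ended by 16 counts before age 15 but not as current status at end line. Until this is settled, a co-primary outcome has two possible values.

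**Working it through.** **1. Inputs.** From the Sample size section: two-sided 5% type 1 error (the two-sided value reproduces the tables), 80% power, m = 28 girls per cluster, k = 0.15, 0.20 or 0.25, control proportion for marriage around 25%, aimed reduction 25-30%. From its summary: 40 clusters per arm. Assumed, because the documents give no figure: b, the share of girls with the event before the intervention.

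**2. Reproducing the plan.** The unmatched cluster-trial formula is

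c = 1 + (1.96 + 0.8416)² × V / (p0 − p1)², with V = p0(1−p0)/m + p1(1−p1)/m + k²(p0² + p1²).

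For p0 = 0.30, p1 = 0.225, k = 0.20: V = 0.0075 + 0.00623 + 0.00563 = 0.01935, and c = 1 + 7.849 × 0.01935 / 0.005625 = 28.0, as printed. All 18 entries of the marriage table reproduce.

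**3. Power with 40 clusters per arm and no earlier events.** Power = Φ(√[39 (p0 − p1)² / V] − 1.96). For p0 = 0.25, p1 = 0.1875, k = 0.20: V = 0.01604, the root is 3.08, and power is 86.9%.

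**4. All girls counted, with earlier events.** The intervention acts on new events only, so p1 = b + 0.75(0.25 − b). For b = 5%: p1 = 0.05 + 0.15 = 0.20, and the ratio is 0.80.

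**5. Event-free girls only.** p0′ = (0.25 − b)/(1 − b), p1′ = 0.75 p0′, m′ = 28(1 − b). The ratio stays at 0.75.

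| b (assumed) | Ratio, all girls | Power, all girls, k = 0.15 / 0.20 / 0.25 | Power, event-free girls, k = 0.15 / 0.20 / 0.25 |
|---|---|---|---|
| 0% | 0.75 | 90.3 / 86.9 / 82.4% | same |
| 1% | 0.76 | 87.7 / 83.9 / 79.0% | 89.1 / 85.6 / 81.1% |
| 2% | 0.77 | 84.7 / 80.5 / 75.2% | 87.8 / 84.3 / 79.8% |
| 5% | 0.80 | 73.0 / 68.1 / 62.4% | 82.8 / 79.3 / 75.0% |

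At k = 0.20, restriction gains 1.7, 3.8 and 11.2 percentage points at b = 1%, 2% and 5%. With a 30% reduction and b = 5%, the all-girls ratio is 0.76 and power is still 87.7 / 83.9 / 79.0%.

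**6. Ended marriages.** If a share d of marriages ends before end line equally in both arms, both proportions are multiplied by (1 − d) and the ratio stays at 0.75. At k = 0.20, power goes from 86.9% to 86.6%, 85.2% or 83.3% for d = 1%, 5% or 10%. If the shares differ between arms, the ratio is multiplied by (1 − d1)/(1 − d0), where d1 is the intervention share and d0 the control share.

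**The case against.** - **The before-age-15 definition already counts an ended early marriage.** True, but the formal outcome list does not use it. The answer shows that the two definitions must be reconciled.
- **The instrument is not visible.** Table 4 lists domains, and the questionnaires are separate documents. A marital status item may have codes for widowed or separated girls. This stands: the reversal follows from the wording, not from a seen skip pattern.
- **Married girls at baseline are not shown.** The consent sentence does not say at which survey round girls are married, and the protocol also expects marriages during follow-up. This stands, so b is purely an assumption and may be very small in girls of about 13 who have just finished 7th standard.
- **Keeping all enrolled girls is a legitimate choice, and adjustment for baseline differences is planned.** Also fair. The detailed handling may sit in an analysis plan.
- **Excluding baseline events could introduce selection in cohort 2.** That cohort enrols a year later, and the intervention's primary stakeholders include girls in 7th standard. Its baseline may therefore follow exposure in the village. This stands and shapes the fix.

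Three stronger readings are tempting. A reader might infer that outcome 4 can also reverse, but it records whether first intercourse has occurred, which cannot be undone. A reader might infer that earlier events bias the test, but villages are randomised, so such events are balanced in expectation and only dilute. A reader might also say that a ratio of 0.76 (a 24% reduction) misses the 25-30% aim. That aim is set for the overall proportion married before 15, and the protocol states no ratio for new marriages alone, so the comparison is not like with like.

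**Conclusion.** The point holds and is minor. Its firmest part is documentary: outcome 3 is current status at end line in the outcome list and marriage before age 15 in the design summary and sizing. Only the current-status version lets an ended marriage count as a success. The numerical cost of ended marriages is small if they are equally common in both arms.

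Counting events that precede the intervention is a real but unquantified loss for outcomes 3 and 4. On the marriage inputs with a 25% reduction in new events, power falls below 80% at an assumed baseline share of about 1% if k = 0.25, between 2% and 3% if k = 0.20, and between 3% and 5% if k = 0.15. If almost no girl has the event at entry, the loss is negligible. These figures assume that the 25% control proportion, which comes from a before-15 survey figure, applies to the outcome analysed and includes the earlier events.

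**What to change.** 1. Define outcome 3 as ever married by end line, or as married before a stated age. Use that one definition in the Summary, outcome list, sizing and analysis.
2. Ask every ever-married girl her age or date at first marriage, whatever her current status.
3. Take new events as the main analysis of outcomes 3 and 4, among girls whose reported age or date of marriage or first sex shows no event before the intervention started in their village. Apply the matching calendar date to control villages, so that the exclusion cannot depend on allocation in cohort 2. Keep the all-girls version as a sensitivity analysis.
4. For outcome 4, use reported age at first sex. Before relying on baseline answers, reconcile Ethical issues, which describes an anonymous paper ballot pooled with others, with the section on biases, which links the self-completed form by serial number.

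The cost is two definitions and one questionnaire item. A few girls leave the denominators of these two outcomes, and ages reported in whole years will date some events only roughly.

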1. Proportion of SC/ST girls in the cohort(s) who pass their matric/class 10 exam
2. Proportion of SC/ST girls in the study cohort who report a change in attitude around gender equality
3. Proportion of SC/ST girls in the study cohort who access available government schemes to assist SC/ST girls to complete secondary school
4. Proportion of SC/ST girls in the study cohort who access tuition classes and/or career counselling at school
5. Proportion of SC/ST girls in the study cohort who have experienced one or more incidents of harassment by boys in the last 3 months: in school; on the way to school; elsewhere in the community.

Process level outcomes

Process level outcomes are intended to understand the pathways from the intervention to the primary and secondary outcomes. They include data collected from the adolescent girls, their families, their schools, and communities:

Adolescent girls:

1. Awareness of the government schemes/subsidies that encourage their education
2. Attendance in tutorial classes
3. Participation in Parivartan Plus group sessions
4. Participation in career counseling to enhance options after school completion
5. Shifts in attitudes and perceived norms among SC/ST girls in the study cohorts and their parents about the value of completing secondary education for girls.
6. Shifts in attitudes and perceived norms among study girl parents about the wisdom of marrying girls before age 18.
7. Shift in attitudes and perceived norms among SC/ST girls in the study cohorts and their parents regarding [some measure of gender equality taken from Parivartan curriculum for boys]
8. Absences from school among the study cohort and proportion of adolescent girls who successfully pass into the next grade (the last element of this outcome would need to be measured using monitoring data for girls not in the cohorts).

Schools/SDMCs/Teachers:

1. Proportion of schools that have developed and implemented action plans to encourage entry and retention of girls in secondary school
2. Proportion of schools that have developed and implemented action plans to make schools safer for girls (anti-harassment, safe toilets, etc)
3. Proportion of surveyed teachers who feel that secondary school education is easily accessible for SC/ST girls in their community
4. Proportion of surveyed teachers who feel that SC/ST girls in their community have the opportunity to continue and complete their secondary

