There will be 13 girls, on average, enumerated for each of two sequential cohorts in each intervention and control cluster. In effect, 26 girls will be enrolled in each cluster, 1 year apart, corresponding to a total sample of 1050 girls in the control arm and 1050 girls in the intervention arm. We assume that there is minimal loss to follow-up and that 28 girls are followed-up at the endline. With these data we will have 80% power to detect a ratio of around 33% for the transition from 7-8th standard and a 25% ratio for retention until 10th standard. We have included conservative estimates of the control outcome proportions, and reported calculations for a range of K from 0.1 to 0.25.

In order to measure the medium- and short-term outcome indicators for families, the families of the SC/ST adolescent girls recruited in both arms will be interviewed. To facilitate intervention at the family level, each SC/ST adolescent girl in both the arms will be profiled and the main decision maker will be identified. These decision makers will form the sampling frame to recruit the respondents at the family level.

The sample sizes for the girls are summarized in Table 3.

Table 3: Summary of sequential cohort study design

	May 2013	May 2014	February 2017	February 2018
Intervention site, cohort 1	525 girls completed 7 th standard and their families		Follow-up interviews	
Control site, cohort 1	525 girls completed of 7 th standard and their families		Follow-up interviews	
Intervention site, cohort 2		525 girls completed 7 th standard and their families		Follow-up interviews
Control site, cohort 2		525 girls completed 7 th standard and their families		Follow-up interviews

Allocation of clusters to intervention and control arms

68 villages were selected using systematic random sampling from the sample frame of 121.

[figure not shown]
Schools were allocated randomly to either receive the intervention immediately (experimental condition) or at a later date (waitlist control group). The villages were randomised into intervention and control arms so that 34 villages (62 high schools) in intervention and 34 villages (63 high schools) in control arms. This was done by initially selecting 34 villages randomly from the selected 68 villages using STATA 11. These selected 34 villages were allocated into intervention arm and the remaining 34 villages were allocated into control arm.

Accounting for potential contamination

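### On the Table 3 dates, the last-3-months and current-use questions behind secondary outcomes 3–5 reach on-time girls about 9 months after 10th standard, so their school-based parts cannot describe standards 8–10

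*Protocol*

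**What the plan says.** **Outcomes (protocol, Outcomes section, secondary outcomes).** Outcome 3 is the proportion of girls "who access available government schemes to assist SC/ST girls to complete secondary school". Outcome 4 is the "Proportion of SC/ST girls in the study cohort who access tuition classes and/or career counselling at school". Outcome 5 is the "Proportion of SC/ST girls in the study cohort who have experienced one or more incidents of harassment by boys in the last 3 months", by setting: "in school; on the way to school; elsewhere in the community". Only outcome 5 states a reference period.

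**How service use is recorded (Table 4, short-term outcomes).** For government schemes: "whether currently availing them, reasons for not availing the services". For tuition: "Whether aware of the mentoring and tutorials at school, and whether currently availing these services". Career counselling has the same form.

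**When girls are interviewed.** The Summary describes a cohort "with a single endline follow up". The dates are in "Table 3: Summary of sequential cohort study design": 7th standard completed in May 2013 (cohort 1) and May 2014 (cohort 2), with follow-up interviews in February 2017 and February 2018. A footnote defines the trial high schools as teaching standards 8, 9 and 10.

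**Other schedules.** Sampling of the adolescent girls ends follow-up of every girl at the opening of study year 4. Time period gives 9 months of start-up, 30 months of intervention and 9 months of final assessment and analysis.

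**Other data on the girls.** Under Process evaluation analysis, service delivery is tracked in the intervention arm. In the control arm, monitoring is limited to a few outcomes such as drop-out and marriage, plus six-monthly visits to confirm where each girl is.

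**The concern.** Two of the three harassment settings, and all of the tuition and counselling outcome, exist only while a girl attends school. Outcome 3 concerns support for completing that same schooling. The baseline interview takes place before high school and the only later one is at endline. If the endline falls after 10th standard and asks about the last 3 months or about current use, a girl who progressed on time has no experience of standards 8–10 left to report. If she is studying further, her answers describe a different institution.

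Tutoring, linkage to government schemes and reducing harassment by boys are named components of the intervention. The secondary outcomes meant to show whether they reached girls, and whether school became safer, would then say little about either arm. Analysis cannot repair this, because the reference period determines what is collected.

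**Working it through.** **Inputs.** The Table 3 dates, three standards (8–10) and the 3-month window of outcome 5 come from the protocol. Twelve months per standard and on-time progression are assumptions.

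**1. Gap between leaving 10th and the interview**

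End of 10th = end of 7th + 36 months. Gap = endline − end of 10th. The window opens at endline − 3 months.

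| | Cohort 1 | Cohort 2 |
|---|---|---|
| End of 7th (Table 3) | May 2013 | May 2014 |
| End of 10th, on time | May 2016 | May 2017 |
| Endline (Table 3) | Feb 2017 | Feb 2018 |
| Months from enrolment to endline | 45 | 45 |
| Gap | 45 − 36 = 9 months | 9 months |
| 3-month window | Nov 2016–Feb 2017 | Nov 2017–Feb 2018 |
| Window opens after end of 10th by | 9 − 3 = 6 months | 6 months |
| Overlap with standards 8–10 | 0 of 3 months | 0 of 3 months |

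If the school year is assumed to end in April or March, the gap becomes 10 or 11 months. A girl who repeated one year would be in 10th until May 2017 (cohort 1) or May 2018 (cohort 2), so her window would still fall in school.

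**2. Do the competing schedules remove the problem?**

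- *Opening of year 4.* If year 1 is assumed to start between January and July 2013, year 4 opens between January and July 2016. That is 32–38 months after enrolment for cohort 1 and 20–26 months for cohort 2. Completing 10th needs 36 months, so cohort 2 could not have done so.
- *9 + 30 months.* From the same range of starts, month 39 falls between April and October 2016. For cohort 1 this runs from 1 month before to 5 months after the end of 10th; for cohort 2 it is 13 to 7 months before.

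Of these schedules, only Table 3 lets co-primary outcome 2 (completing 10th) be observed in both cohorts. It is the one to test the secondary outcomes against.

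**3. Is there another source for the between-arm comparison?**

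- Baseline survey of girls: before high school.
- Family survey (Table 5): also asks about the girl's present use of services.
- Monitoring: records services in the intervention arm; the control arm has a few outcomes such as drop-out and marriage.
- Six-monthly control visits: their stated aim is to confirm availability.

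None supplies harassment at school, tuition, counselling or scheme use during standards 8–10 for both arms of the cohort.

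**The case against.** **Current use is not in the outcome definitions.** Correct. Outcomes 3 and 4 give no reference period; the present-tense form comes from Table 4, which summarises domains. The questionnaires are separate documents, and the appendix that lists them is titled for baseline. Table 4 also asks about life-skills sessions in a past form. So it cannot be stated as fact that outcomes 3 and 4 will be near zero at endline; that follows only if the endline items keep the Table 4 wording. The 3-month window of outcome 5 does not have this uncertainty.

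**The timing rests on one of several schedules.** Also correct, and the protocol needs to reconcile them. The alternatives do not rescue the outcomes, because they leave cohort 2 short of completing 10th.

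**A reader might infer that the gap biases harassment against the intervention.** With 30% control drop-out and a 25% reduction, retention is 70% against 77.5%, and 0.775/0.70 = 1.11. This does not measure the timing problem. It arises from using the whole cohort as denominator when more intervention girls stay in school, and would appear equally if girls were asked during 10th.

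**A reader might also infer that study questions 3 and 4 cannot be answered.** The protocol does not support that. Question 3 is served by surveys of principals, teachers and school committee members in both arms and by interviews. Question 4 lists value for education, self-esteem, perceived safety and status, and norms, not tuition or scheme use. Lifeline case studies (20 intervention and 10 control girls) follow girls for 3 years from 8th and cover school events and schemes.

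**Asking only girls who entered 8th would introduce bias.** This stands: entry is co-primary outcome 1, so that restriction conditions on something the intervention aims to change. The fix must avoid it.

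**Conclusion.** The point holds within limits. On the Table 3 schedule, a girl progressing on time is interviewed about 9 months after completing 10th standard (10–11 if the school year ends in April or March). The in-school and way-to-school parts of outcome 5 then overlap standards 8–10 by 0 of 3 months in both cohorts. The Table 4 current-use items feeding outcomes 3 and 4 cannot describe those years either, and no control-arm source replaces them.

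This rests on 12-month standards, on-time progression, Table 3 being the operative schedule and, for the service items, endline wording that follows Table 4. Harassment elsewhere in the community remains measurable, repeaters may still be in 10th, and no co-primary outcome is affected. It should be corrected before the endline instruments are fixed, as a weakness in secondary outcomes rather than a threat to the main comparison.

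**What to change.** 1. Keep the endline date, which completion of 10th requires, and reconcile the year-4 statement in Sampling of the adolescent girls with Table 3.
2. Define secondary outcomes 3 and 4 as ever having used the scheme, tuition or counselling during standards 8–10, and record in which standard. Align Table 4 and the endline questionnaire.
3. For outcome 5, ask about harassment in school and on the way to school with reference to the time the girl attended standards 8–10. Keep the last 3 months for elsewhere in the community.
4. Use identical wording in both arms.
5. Analyse the primary version of each outcome in the full cohort, including girls who never entered 8th. Report results among attenders as descriptive only. State in advance that a whole-cohort school-harassment proportion rises with retention, so it must be read beside the retention result.

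The cost is rewording a few endline items and three outcome definitions. The drawback is longer recall: at least 9 months for on-time completers and longer for early drop-outs. The mix of recall lengths may differ between arms if retention does.
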